11.3.2 Workstream 3b

We will use the full augmented WS2a data set (the retrospective cohort) for model development, which will be approximately 293,200 women. Assuming a conservative event rate of 2% (as in WS2a), a c-statistic of 0.8, and a shrinkage factor of 0.9, we will be able to include more than 850 parameters in our model if using logistic regression (which is more than adequate) (75).

After development we will assess the performance of our model in the prospective cohort within key sub-groups (including maternal age and ethnicity). The prospective cohort will include the births from up to 12 sites over a period of two years and four months, and therefore will be approximately 164,300 in total. The national MBRACE report shows the proportion of women in the different ethnic groups (White 79.5%, Asian 10.3%, Black 4.3%, Chinese 4.1%, Mixed 1.8%) (17). Working with the NIHR HIC, we will ensure that we have at least this degree of representation in our research database. We would therefore expect event rates of greater than 100 (the minimum recommended in TRIPOD guidance and quoted papers) (74) for all groups other than “Mixed” (White 2611, Asian 338, Black 141, Chinese 134, Mixed 59) assuming a flat 2% event rate. If higher event rates are seen in the different groups as reported (relative risk Asian 1.8 95% CI (1.2-2.7), Black 4.9 (3.3-7.3), Mixed 2.0 (0.7-4.9)) (5) we will have over 200 events in major groups.

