3 SYNOPSIS

| | |
|---------------------------------|---|
| Study Title | Defining, Recognising and Escalating Maternal Early Deterioration (DREaMED) Phase 1: Decreasing inequality through improved outcomes |
| Internal ref. no. / short title | DREaMED1 |
| Study registration | The study will be registered on clinicaltrials.gov |
| Sponsor | University of Oxford |
| Funder | National Institute for Health and Care Research (NIHR), Programme Grants for Applied Research (NIHR204430) |
| Study Design | Longitudinal Cohort study |
| Study Participants | Women aged 16 or over who are pregnant |
| Sample Size | Total: 459,160 Retrospective cohort: 293,200 Prospective cohort: 164,300 MBRRACE-UK cohort: 1,300 Patient interviews (escalation pathway): Up to 60 Staff interviews/focus groups (escalation pathway): Up to 100 Staff interviews/focus groups (eMOEWS interface development): Up to 100 Staff training (simulation scenarios): Up to 100 |
| Planned Study Period | Funded study period: 02/05/2023 until 01/05/2029 Total funded study period will be 6 years Planned study period: 01/05/2024 until 01/05/2029 |

| Planned Recruitment period | Retrospective cohort: 01/01/2021 to 28/02/2025 Prospective cohort: 01/03/2025 to 30/06/2027 MBRRACE-UK cohort: 01/01/2009 to 31/12/2022 Staff interviews/focus groups (eMOEWS interface development, WS4a): 01/04/2025 to 31/03/2026 Patient interviews (escalation pathway, WS4b): 1/06/2024 to 30/08/2025 Staff interviews/focus groups (escalation pathway, WS4b): 01/06/2024 to 30/11/2025 Staff training (simulation scenarios, WS4c): 01/11/2026 to 30/11/2027 | | |
|----------------------------|--|--|---|
| | Objectives | Outcome Measures | Timepoint(s) |
| Primary | To develop, and validate an electronically-embedded, data-enhanced Maternal Early Warning Score (eMOEWS) with clinical escalation pathways | Predictive performance of new early warning scores, assessed by: discrimination, calibration, and clinical utility. | During pregnancy or in the immediate postpartum period. |
| Secondary: | | | |
| | To define 'near-miss' and 'pre-near-miss' criteria for use with routinely-collected data to measure maternal outcomes | 'Near-miss' and 'pre-near-miss' outcome criteria measurable using routinely available electronic data, assessed in NHS hospitals | During pregnancy or in the immediate postpartum period. |

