7.4.2 Workstream 3b – developing an optimal vital-signs MOEWS and multivariable eMOEWS

We will develop and externally validate (see Section 11.2.4 for further details):

- A vital-signs-based MOEWS for use in environments where connection to an EPR is not available.
- A multivariable electronic maternal early warning score (eMOEWS) for use in digitally mature environments

We will extract a separate, more recent 2-year validation cohort from eight-twelve sites to allow external validation (containing relevant variables) of the optimal vital-signs MOEWS and multivariable eMOEWS.

7.5 Workstream 4

In Workstream 4 we will:

- Build working eMOEWS web interfaces following user-centred design principles (Workstream 4a).
- Develop escalation and response pathways for women identified as at risk by the eMOEWS (Workstream 4b)

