We will explore risk thresholds to identify high risk (such that we predict poor outcome) and low risk (such that we predict good outcome) groups. We will compare performance of our models to those of published MOEWSs established in WS2a, including decision curve analysis. We will externally validate our models using new data from our collaborator sites collected in the two years following the derivation cohort. We will assess the model performance within key pre-defined sub-groups (including maternal age and ethnicity).

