11.3 Sample Size Determination

11.3.1 Workstream 2a

We estimate the WHO “near-miss” event rate will be at least 10/1000 (2,3) and the severe morbidity event rate will be at least a further 10/1000 maternities (2,73) . Although rates of our less severe new ‘pre-near-miss’ will be higher we have calculated our sample size based on these severe event rates alone. The retrospective cohort will include four years and two months' worth of data from up to 12 sites. We anticipate that there will be 5875 births on average per site per year. Therefore, we will have approximately 293,200 births in the retrospective cohort, of whom 2932 will have a near-miss and at least a further 2932 will have pre-near-miss events. Guidance suggests that at least 100 events are required for model validation (74). Therefore, our sample size (which is driven both by the need for adequate representation in subgroups and the requirements of WS3, see below) should be more than sufficient to generate robust performance metric estimates, including in key subgroups and for the secondary outcomes (see model performance in key subgroups WS3b below – note that the retrospective cohort is larger than the prospective cohort and therefore the number of events per subgroup will be even higher).

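### Section 11.3.2 counts validation subgroup events over 28 months at the 12-site maximum, while 7.4.2 and 11.2.4.3 set external validation on two years of data, from eight to twelve sites

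*Protocol*

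**What the plan says.** **Period.** Section 7.4.2 states: "We will extract a separate, more recent 2-year validation cohort from eight-twelve sites". Section 11.2.4.3 agrees, placing the external validation data as those "collected in the two years following the derivation cohort". Section 11.3.2 assesses the models in the prospective cohort and describes it differently: "The prospective cohort will include the births from up to 12 sites over a period of two years and four months". The synopsis dates that cohort "Prospective cohort: 01/03/2025 to 30/06/2027", which is 28 months. Section 8.1.2 says that the model validation dataset and the real-time platform testing dataset both lie within the prospective cohort.

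**Sites.** The design is eight to twelve maternity units (Sections 2, 3, 6, 7.3, 7.4.1.3 and 7.4.2). Section 11.3 sizes both cohorts from at most 12 sites, using this input: "We anticipate that there will be 5875 births on average per site per year". The synopsis lists "Total: 459,160 Retrospective cohort: 293,200 Prospective cohort: 164,300 MBRRACE-UK cohort: 1,300" with no sign that the two cohort sizes are maximums, although the interview, focus group and training samples beside them are marked 'up to'.

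**Subgroups.** Section 11.3.2 gives the ethnic shares and, at a flat 2% event rate, expects White 2611, Asian 338, Black 141, Chinese 134 and Mixed 59 events. It concludes: "We would therefore expect event rates of greater than 100 (the minimum recommended in TRIPOD guidance and quoted papers) (74) for all groups", excepting Mixed. On the shares it adds: "we will ensure that we have at least this degree of representation in our research database".

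**The concern.** The subgroup counts in 11.3.2 are presented as those of the external validation. They use 28 months where two other sections say two years, and the top of a site range that 7.4.2 applies to the validation cohort itself. If the validation set is a two-year part of the prospective cohort, which 8.1.2 would allow, the counts belong to a larger dataset than the one to be analysed.

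Checking performance by ethnicity is a stated validation aim, 11.3.1 names subgroup representation as one driver of the sample size, and the protocol adopts 100 events as its minimum. A reader cannot tell from the text which dataset the minimum is judged on, or whether it is met at fewer than 12 sites.

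**Working it through.** **Inputs, all from the protocol**
- Births per site per year: 5875, an average (11.3.1)
- Sites: 8 to 12 (7.4.2)
- Months: 28 (11.3.2 and synopsis dates) or 24 (7.4.2, 11.2.4.3)
- Event rate: 2%, flat (11.3.2)
- Shares: White 79.5%, Asian 10.3%, Black 4.3%, Chinese 4.1%, Mixed 1.8% (11.3.2)
- Minimum: 100 events per group (11.3.1, 11.3.2)

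**Formulas**
- Births = sites × 5875 × months / 12
- Events in a group = births × 0.02 × share
- Births needed for 100 events = 100 / (0.02 × share)

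**Reproducing the stated figures**
- Retrospective: 12 × 5875 × 50/12 = 293,750 (stated 293,200)
- Prospective: 12 × 5875 × 28/12 = 164,500 (stated 164,300)
- Events at 164,300 births: White 2612, Asian 338, Black 141, Chinese 135, Mixed 59, matching the stated counts to rounding
- Synopsis total: 293,200 + 164,300 + 1,300 + 60 + 3 × 100 = 459,160, as stated

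The cohort sizes therefore reproduce, with all 12 sites.

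**Births needed for 100 events**
- Black: 100 / (0.02 × 0.043) = 116,279
- Chinese: 100 / (0.02 × 0.041) = 121,951

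Chinese women are the limiting group. One site yields 5875 × 28/12 = 13,708 births over 28 months or 11,750 over 24. So 121,951 births need 8.90 sites (9) over 28 months or 10.38 sites (11) over 24.

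**Across the planned range**

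| Months | Sites | Births | Black | Chinese | Mixed |
|---|---|---|---|---|---|
| 28 | 8 | 109,667 | 94 | 90 | 39 |
| 28 | 9 | 123,375 | 106 | 101 | 44 |
| 28 | 12 | 164,500 | 141 | 135 | 59 |
| 24 | 8 | 94,000 | 81 | 77 | 34 |
| 24 | 9 | 105,750 | 91 | 87 | 38 |
| 24 | 10 | 117,500 | 101 | 96 | 42 |
| 24 | 11 | 129,250 | 111 | 106 | 47 |
| 24 | 12 | 141,000 | 121 | 116 | 51 |

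White and Asian exceed 100 throughout; the smallest Asian count is 94,000 × 0.02 × 0.103 = 194.

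**How close the shortfall is, at 8 sites**
- Event rate giving 100 Chinese events: 100 / (109,667 × 0.041) = 2.22% over 28 months; 100 / (94,000 × 0.041) = 2.60% over 24
- Share giving 100 events at 2%: 100 / (109,667 × 0.02) = 4.56% over 28 months; 100 / (94,000 × 0.02) = 5.32% over 24

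**Retrospective cohort at 8 sites:** 8 × 5875 × 50/12 = 195,833 births, giving Black 168 and Chinese 161 events. It is not affected.

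**The case against.** The strongest reply is that 11.3.2 prints its conditions: at most 12 sites, an average number of births, and a flat 2% rate that it calls conservative. Under those conditions the numbers are right. A reader might infer an arithmetic error; there is none.

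A reader might also infer that the synopsis contradicts the two-year validation outright. It does not. It dates the prospective cohort, not the validation period, and 8.1.2 leaves room for a two-year validation set inside a 28-month cohort. What remains is that 11.3.2 counts validation subgroup events over all 28 months. On the subset reading those counts are for the wrong dataset; on the whole-cohort reading, 7.4.2 and 11.2.4.3 give the wrong period.

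The inputs are also floors. The outcome in 7.3.3.3 includes pre-near-miss events, whose rates 11.3.1 expects to be higher than those used. As an illustration only, since the criteria are not yet fixed, Section 5.2 cites haemorrhage of 1500 ml or more in up to 3.3% of women. At that rate even 8 sites over 24 months would give 94,000 × 0.033 × 0.041 = 127 Chinese events. The shares are minimums, and those of the smaller groups could all rise if the White share fell. For Black women, the morbidity up to 70% higher in Section 5.1 would give about 160 events (28 months) or 137 (24 months) at 8 sites. Section 11.3.2 gives no relative risk for Chinese women.

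Finally, no decision rule hangs on 100 events, and the protocol already accepts 59 for Mixed. If standard errors scale with one over the root of the event count (an assumption), 90 events widen intervals by about 5% and 77 by about 14% relative to 100.

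These replies limit the size of the problem. They do not settle which period applies, and the more-than-100 statement is itself made at 2%.

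**Conclusion.** The point holds as an inconsistency between sections and a conclusion stated more widely than the design supports. The two-year validation set of 7.4.2 and 11.2.4.3 is not the dataset that 11.3.2 sizes: at 12 sites it would be 141,000 births rather than 164,500. The more-than-100 statement is true at 12 sites on either period. It fails at 8 of the 8-12 sites over 28 months and at 8, 9 and 10 sites over 24 months; at 10 sites only Chinese women fall short.

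This rests on 5875 births per site per year at any number of sites, the stated shares and a flat 2%. All three are the protocol's figures, and the last two are floors. It would be too strong to conclude that subgroup validation is inadequate: the shortfall is modest, sits at the low end of the inputs, and leaves the retrospective cohort untouched.

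**What to change.** 1. Reconcile 24 and 28 months in 7.4.2, 11.2.4.3 and 11.3.2, and say whether the validation set is the whole prospective cohort or a two-year part of it.
2. In 11.3.2, restate the validation size and subgroup counts for that dataset as 8-12 site ranges:
   - 28 months: about 109,700-164,500 births; Black 94-141, Chinese 90-135, Mixed 39-59
   - 24 months: 94,000-141,000 births; Black 81-121, Chinese 77-116, Mixed 34-51

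   Limit the more-than-100 statement to at least 9 sites over 28 months, or 11 over 24, at a 2% rate.
3. Mark the cohort sizes and the total in the synopsis as 'up to'.

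The cost is wording. No extra sites or women are needed; the only downside is that the stated figures look less favourable.

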5 BACKGROUND AND RATIONALE

5.1 What is the problem being addressed?

Of over 700,000 women giving birth in the UK annually, one in every 10,000 women dies during or up to six weeks after pregnancy (1). For every woman that dies, 120 will have a 'near-miss' (8,700 women annually) often with lifelong sequelae (2). Recent data from the United States using adapted Centre for Disease Control definitions found even higher rates (2%) (3). There are significant disparities in maternal and perinatal outcomes between ethnic, age and socioeconomic groups (1,4). Maternal mortality has been consistently shown to be more than four-fold higher among women from Black ethnic groups, and two-fold higher among women from Asian ethnic groups compared to women from White ethnic groups (5). Mortality rates are similarly two-fold higher amongst women who live in the 20% most deprived areas compared to those who live in the least deprived areas (5). Women aged over 40 are four times more likely to die during or after pregnancy compared to women aged 25-29 (5). Substantial disparities also exist in severe maternal morbidity; a recent analysis by our group (manuscript submitted) using Hospital Episodes Statistics data has shown that severe maternal outcomes at the time of a childbirth event, measured using the English Maternal Morbidity Outcome Indicator (EMMOI) are up to 70% higher amongst women from Black Caribbean and Black African ethnic groups. This disparity persists across all English regions and is driven primarily by sepsis and complications related to haemorrhage or pre-eclampsia. This variability, along with the major underlying causes, suggest a high degree of avoidability, a suggestion strongly supported by MBRRACE-UK mortality reports (5).

Current published morbidity criteria (6-9) represent near end stage (near death), rather than early deterioration and are not reliably derivable from routine data, preventing both development of early warning systems to detect early maternal deterioration and effective routine quality assurance.

The detection of women at risk of severe maternal morbidity or mortality is currently limited by the use of expert opinion-based Modified Obstetric Early Warning Scores (MOEWS). These MOEWS are based only on the most recent set of vital signs (heart rate, blood pressure, oxygen saturation, respiratory rate,

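### The claim of over 200 events in major ethnic groups rests on what appear to be maternal-death ratios applied to near-miss and severe-morbidity events; for Black women it holds only if the true ratio is at least about 1.42

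*Protocol*

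**What the plan says.** Section 11.3.2 of the protocol sizes the prospective validation cohort by ethnic group. It takes births from up to 12 sites over two years and four months, which "therefore will be approximately 164,300 in total", and splits them by national shares: "White 79.5%, Asian 10.3%, Black 4.3%, Chinese 4.1%, Mixed 1.8" per cent. Expected events are then counted "assuming a flat 2% event rate": White 2611, Asian 338, Black 141, Chinese 134, Mixed 59. Every group except Mixed passes the stated minimum of 100.

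A second, conditional sentence follows. If rates differ between groups as reported in reference 5 ("relative risk Asian 1.8 95% CI (1.2-2.7), Black 4.9 (3.3-7.3), Mixed 2.0 (0.7-4.9"), then "we will have over 200 events in major groups". The section does not say which outcome these ratios describe, and it does not define the major groups.

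Section 11.3.1 builds the 2% from a near-miss rate of at least 10 per 1000 and a severe-morbidity rate of at least a further 10 per 1000.

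Section 5.1 also cites reference 5: "Maternal mortality has been consistently shown to be more than four-fold higher among women from Black ethnic groups", and two-fold higher among Asian women, each compared with White women. The same paragraph gives a separate figure for severe maternal outcomes, from the team's own analysis of hospital data: "up to 70% higher amongst women from Black Caribbean and Black African ethnic groups".

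**The concern.** The ratios and the events they multiply appear to belong to different outcomes. Section 5.1 uses reference 5 for deaths, and its sizes for Black and Asian women agree with 4.9 and 1.8. The events counted in section 11.3.2 are near-misses and severe morbidity. Section 5.1 puts maternal death at one in 10,000, so a 2% outcome is 0.02 / 0.0001 = 200 times as common. A ratio for the rare outcome need not carry over to the common one, and the protocol's own morbidity figure suggests that it does not: at most 1.7 for Black women, whereas even the lower confidence limit of the ratio used is 3.3. Applied to 2%, 4.9 means that 9.8% of Black women would have an event.

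Reducing inequality is a stated aim of the programme, and section 11.3.1 relies on the same paragraph for subgroup performance in Workstream 2a. A reader would take from it that events in Black women will be plentiful. The better-matched figure leaves a thin margin that depends on the number of sites.

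**Working it through.** **Inputs.** Cohort 164,300; shares as listed above; base rate 2%; ratios 1.8, 4.9 and 2.0 (all section 11.3.2). Births per site: "We anticipate that there will be 5875 births on average per site per year" (section 11.3.1). Morbidity ratio for Black women: at most 1.7 (section 5.1). Number of sites: eight to twelve (sections 7.3 and 7.4.2).

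**Step 1: reproduce the plan's figures.** Cohort: 5875 × 12 × 28/12 = 164,500, against 164,300 stated. Events per group = 164,300 × share × 0.02:

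| Group | Stated | Flat 2% | Ratio in 11.3.2 | Events with that ratio |
|---|---|---|---|---|
| White | 2611 | 2612 | reference | 2612 |
| Asian | 338 | 338 | 1.8 | 609 |
| Black | 141 | 141 | 4.9 | 692 |
| Chinese | 134 | 135 | none given | 135 |
| Mixed | 59 | 59 | 2.0 | 118 |

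The flat counts reproduce to within rounding. With the stated ratios, White, Asian and Black exceed 200, while Chinese and Mixed do not. The claim therefore works only if the major groups are those three.

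**Step 2: which groups need a ratio to pass 200.** White and Asian pass at the flat 2%. Black is the only group that the ratio carries across 200.

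**Step 3: Black women with the protocol's morbidity figure.** The flat count is 164,300 × 0.043 × 0.02 = 141.3.
- Ratio 1.0: 141
- Ratio 1.2: 170
- Ratio 1.4: 198
- Ratio 1.5: 212
- Ratio 1.7: 240
- Ratio 4.9: 692

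The ratio needed for 200 events is 200 / 141.3 = 1.42. At the upper value of 1.7, the count is 1 − 240/692 = 65% below the figure implied by 4.9.

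**Step 4: eight sites instead of twelve.** Births: 5875 × 8 × 28/12 = 109,667. Black events at the flat rate: 109,667 × 0.043 × 0.02 = 94.3; at 1.7, 160. Reaching 200 would need 200 / 94.3 = 2.12, above anything the morbidity figure allows. At 4.9 the count would be about 462, so the larger ratio hides the dependence on site number.

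**Step 5: Mixed and the 100 threshold.** The flat count is 59. Passing 100 needs 100 / 59.1 = 1.69. The ratio 2.0 gives 118, but its stated interval (0.7 to 4.9) includes 1, and section 5.1 gives no morbidity ratio for this group.

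**The case against.** The strongest reply is that little depends on this sentence. The adequacy criterion is the one before it: more than 100 events per group at a flat 2%, with no ratio used and Mixed openly excepted. The sentence at issue is conditional. That is correct, and the 100-event criterion at 12 sites stands. A reader might infer that the subgroup sample size fails; the protocol does not support that.

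A reader might also infer that the 200 figure collapses once the ratio is corrected. It does not. White and Asian pass without a ratio, and Black reaches 240 at 1.7 with 12 sites. What is lost is the margin, because 1.7 is an upper value.

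A third tempting reading is that multiplying ratios onto 2% counts the excess twice, because the group rates then average more than 2%. The protocol presents 2% as a conservative minimum and nowhere requires the groups to average to it, so that charge is not established.

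Two further replies have weight. The 2% is a floor: section 11.3.1 expects pre-near-miss rates to be higher, and section 7.3.3.3 includes those events in the primary outcome for assessing existing scores. Section 5.2 cites up to 3.3% for postpartum haemorrhage of 1500 ml or more. If the composite rate were 3.3% (an assumption), Black events would be 7,065 × 0.033 = 233 with no ratio. Also, the 1.7 comes from an indicator measured at childbirth, which is not exactly the outcome counted, so it is a closer proxy than mortality rather than an exact match. Neither reply justifies using a mortality ratio.

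Finally, the shortfall at eight sites is partly a matter of site number: the flat count there is already 94.

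**Conclusion.** The input is wrong as written, and the consequence is minor. On a 2% base, expected events in Black women are 141 to 240 at 12 sites, not about 692; they exceed 200 only if the ratio is at least about 1.42. At eight sites the range is 94 to 160, below 200 throughout. White and Asian exceed 200 regardless, Chinese does not, and Mixed passes 100 only through the 2.0.

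This rests on three assumptions. The ratios are taken to be mortality ratios because section 5.1 cites the same reference for mortality at matching sizes; section 11.3.2 does not label them. The morbidity ratio for Black women is taken to lie between 1.0 and 1.7. The 2% base, the ethnic shares and the births per site are taken as the protocol gives them; a higher event rate would raise every count.

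**What to change.** In section 11.3.2:
- Remove the mortality ratios from the event calculation, or label them as mortality ratios and do not multiply by them.
- Restate expected events in Black women as about 141 to 240 at 12 sites on a 2% base rate, with 94 to 160 at eight sites.
- Keep the flat 2% for groups for which the protocol has no morbidity ratio.
- Replace the undefined major groups with named ones. At 12 sites and a flat 2%, White and Asian exceed 200; Black and Chinese exceed 100; Mixed does not reach 100. Add that Black exceeds 200 only at a ratio of about 1.42 or more.

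The overall rate need not be held at exactly 2%. With Black at 1.7 and the other groups flat it becomes 0.957 × 2% + 0.043 × 3.4% = 2.06%, which is compatible with 2% as a minimum.

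The cost is protocol wording and a less favourable statement of subgroup size. Data collection, cohort size and analysis methods do not change.
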